7.5.6 End of Treatment Visit

At the early discontinuation of AR101 dosing (for subjects who discontinue early) or at the end of AR101 treatment, subjects will return to the clinic for the End of Treatment visit. A DBPCFC (Appendix 11) will be performed for all subjects except those who discontinue early for safety reasons. AR101 will not be administered on the days of the DBPCFC. AR101 dosing will continue until the last food challenge is performed.

The following procedures will be performed before the DBPCFC:

- TRACK questionnaire (for subjects aged 1 to < 5 years with asthma only; completed by the parent/caregiver)
- C-ACT (for subjects aged \geq 5 years with asthma only) (complete before PEF)
- Weight, height
- Vital signs
- PEF (for subjects aged ≥ 4 years) (should be measured at approximately the same time of day at each visit assessment)
- Asthma evaluation
- EASI score
- Complete physical examination
- Food allergen exposure update
- Monitoring and recording of AEs, including allergy symptoms
- Concomitant medication review
- Diary log review
- Return of unused AR101
- AR101 dosing compliance check
- Blood sample collection:
 - CBC (if not completed within prior 6 months)
 - Immunology assessments

- SPT
- Completion of questionnaires:
 - FAQLQ and FAIM
 - FAQL-PB
- PEESS v2.0 (for subjects who had GI AEIs)

The following procedures will be performed before discharge from the clinic:

- Monitoring and recording of AEs, including allergy symptoms
- Peanut allergy training

At the end of the End of Treatment visit, the investigator must advise the subject's parent/caregiver of appropriate options for continued management of peanut allergy.

Site staff will contact the subject's parent/caregiver by telephone at least 14 days after the last AR101 dose or last food challenge, whichever is last, to enquire if any AEs (including allergy symptoms, GI symptoms, and accidental/nonaccidental food allergen exposure) occurred after the subject left the clinic and to provide assistance in management of events.

7.5.7 Unscheduled Visit

A subject may return to the clinic between scheduled visits to have the AR101 dose adjusted, because of AEs or lack of tolerance to the current dose regimen or for other reasons as required by the investigator.

The procedures performed at unscheduled visits may include any or all of those listed in Appendix 5.

7.5.8 Unscheduled Blood Sample

An unscheduled blood sample for CBC and immunologic assessments may be collected around the time of the last dose of AR101 during a scheduled or unscheduled visit for subjects who intend to discontinue dosing; a blood sample will not be required at the End of Treatment visit if this unscheduled blood sample is collected.

7.5.9 Follow-Up Observation Period

The End of Treatment visit will be followed by a 12-month observation period (Appendix 6). During observation, management of peanut allergy will be guided by the subject's physician. Observation assessments will be conducted by telephone at 3, 6, and 9 months to enquire about the following:

- Current treatment plan
- Key events review

7.5.10 Study Exit Visit

The Study Exit visit will be conducted at 12 months after the last dose of AR101 (Appendix 6). An optional DBPCFC may be performed.

The following procedures will be performed:

- Verification of informed consent/assent for participation in the DBPCFC
- Height, weight
- Vital signs
- PEF (for subjects aged \geq 4 years)
- Current treatment plan
- Key events review
- Abbreviated physical examination
- Blood sample collection for immunology assessments
- SPT
- FAQLQ and FAIM questionnaires

After completing these procedures, a DBPCFC will be performed for subjects who consent.

8 ADVERSE EVENTS AND SAFETY MONITORING

8.1 Definitions

8.1.1 Adverse Event

An AE is any untoward medical occurrence in humans, whether or not considered related to the IP, that occurs during the conduct of a clinical study. Any change in clinical status, electrocardiograms, routine laboratory results, x-rays, physical examinations, etc, that is considered clinically significant by the study investigator is considered an AE.

In addition, any pregnancy diagnosed in a female subject during treatment with an IP will be collected as an AE. The pregnancy will be reported to the Safety Reporting Center within 24 hours of knowledge of the pregnancy.

8.1.2 Adverse Reaction

A suspected adverse reaction is any AE for which there is a reasonable possibility that the IP caused the AE. A reasonable possibility implies that there is evidence that the IP caused the event.

An adverse reaction is any AE caused by the IP.

8.1.3 Serious Adverse Event

An SAE is any event that results in any of the following outcomes:

- 1. Death
- 2. Life-threatening AE (life-threatening means that the study subject was, in the opinion of the investigator or sponsor, at immediate risk of death from the reaction as it occurred)
- 3. Inpatient hospitalization or prolongation of existing hospitalization
- 4. Persistent or significant incapacity or substantial disruption of the ability to conduct normal life functions
- 5. Congenital abnormality or birth defect
- 6. Important medical event that may not result in one of the above outcomes, but may jeopardize the health of the study subject or require medical or surgical intervention to prevent one of the outcomes listed in the above definition of serious event

It is anticipated that the most likely cause of SAEs in this study will be anaphylaxis; however, not all occurrences of anaphylaxis are necessarily SAEs.

8.1.4 Adverse Event of Interest

AEIs include anaphylaxis, GI AEs with prolonged dose interruption (> 7 consecutive days) or that result in early discontinuation, accidental and nonaccidental food allergen exposure, severe adverse events, and use of epinephrine. Allergic reactions during food challenges will not be considered related to study product or reported as AEIs.

AEIs will be reported to the Safety Reporting Center within 24 hours of the study site personnel's knowledge of the event, regardless of the investigator assessment of the relationship of the event to study product.

8.1.4.1 Anaphylaxis

Anaphylaxis and systemic allergic reaction are synonymous terms in this study. In AR101 clinical program reporting (eg, in the AR101 investigator brochure), anaphylaxis refers only to *severe* systemic allergic reactions.

Anaphylactic AEs will be considered AEIs. Anaphylaxis is defined by a number of signs and symptoms that occur alone or in combination within minutes up to a few hours after exposure to a provoking agent. Anaphylaxis can be mild, moderate, or severe in this study. Most cases are mild, but any event of anaphylaxis has the potential to become life-threatening. The clinical criteria for defining anaphylaxis have been adopted for this study from the second symposium on the definition and management of anaphylaxis of the National Institute of Allergy and Infectious Diseases/Food Allergy and Anaphylaxis Network (Sampson, 2006), and are consistent with the international consensus on anaphylaxis (Simons, 2011).

The clinical criteria for suspected anaphylaxis are defined in Appendix 7 and the severity grading parameters are provided in Appendix 8. When the diagnosis of anaphylaxis is made, the basis for suspecting the diagnosis must be documented using these criteria.

With respect to the inclusion of being potentially life-threatening in the definition of anaphylaxis and how that relates to the assessment of anaphylaxis as an SAE, reference is made to the Definitions and Standards for Expedited Reporting in the ICH E2A Tripartite Guideline, which states the following:

An adverse event or suspected adverse reaction is considered life-threatening if, in the view of either the investigator or sponsor, its occurrence places the subject at immediate risk of death. It does not include an adverse event or suspected adverse reaction that, had it occurred in a more severe form, might have caused death.

Thus, for the reporting of anaphylaxis as an SAE, the severity of the reaction, assessed according to the European Academy of Allergy and Clinical Immunology (EAACI) system for grading the severity of anaphylactic reactions (Muraro, 2007), is also to be taken into account (Section 8.2.2.1 and Appendix 8).

8.1.4.2 Gastrointestinal AEs Resulting in Prolonged Interruption of Dosing

Gastrointestinal AEs, typically chronic/recurrent GI AEs, that result in prolonged interruption of dosing will also be considered AEIs and will be assessed longitudinally according to the procedures described below. EoE presents with varied symptoms of esophageal dysfunction that differ between children and adults (Dellon, 2011; Dellon, 2013). In children, the symptoms are often nonspecific and may include feeding difficulties, failure to thrive, abdominal pain, regurgitation, nausea, and vomiting. In adults, the most frequent symptoms are dysphagia and food impaction; less frequent symptoms include heartburn, chest pain, abdominal pain, nausea, or vomiting. Special attention should be paid to these symptoms, which may suggest esophageal dysfunction, particularly when the symptoms are new in onset during the study, chronic or recurrent, or experienced as a complex of multiple symptoms.

To delineate these AEIs, prolonged interruption of dosing is defined as withholding AR101 for > 7 days. This will include 3 categories of subjects:

- Any subject whose dose is withheld for > 7 days due to GI AEs and resumes dosing at a reduced dose level
- Any subject who develops chronic/recurrent GI AEs at or before reaching the 20 mg dose level and resumes dosing after a 30-day dosing hiatus
- Any subject who experienced GI AEs and discontinues early from the study

Subjects with GI AEIs will be asked to complete the PEESS v2.0 questionnaire (Franciosi, 2011) while the subject is symptomatic, at the End of Treatment visit, and then monthly for 6 months thereafter. Parents/caregivers will also complete the PEESS v2.0 as appropriate. It should be noted that the PEESS v2.0 was not designed to establish a diagnosis of EoE; the use of the PEESS v2.0 to monitor the clinical course of GI symptoms must be

considered exploratory. However, the PEESS v2.0 has shown content and construct validity (Franciosi, 2011; Martin, 2015) and holds promise for being a valuable tool to follow the clinical course of EoE or an EoE-like immune-mediated GI syndrome. The PEESS v2.0 could reveal trends toward symptomatic improvement or worsening that might otherwise go undetected.

Subjects who discontinue AR101 treatment early due to chronic/recurrent GI AEs will be requested to return to the clinic for evaluation monthly for at least 6 months (if the subject is asymptomatic, telephone follow-up with a physician investigator may substitute for in-clinic visit, at the investigator's discretion). If chronic/recurrent GI AEs persist beyond 6 months, subjects will continue to be followed with monthly clinic visits (telephone follow-up with an investigator may substitute for in-clinic visit, at the investigator's discretion) until the symptoms have resolved or are assessed to have stabilized with optimal medical management.

If chronic/recurrent GI AEs do not completely resolve within 6 weeks after discontinuation of AR101 dosing, the subject should be referred to a (pediatric) gastroenterologist. Subjects with EoE confirmed by biopsy will have safety follow-up monthly for at least 6 months or until resolution of symptoms and/or tissue eosinophilia, whichever is last.

If a subject who discontinued AR101 treatment early due to chronic/recurrent GI AEs is unable to discontinue the use of symptomatic therapies initiated to treat the GI AEs (eg, H1 or H2 histamine blockers or proton pump inhibitors) by 12 weeks from the time that AR101 was discontinued, the subject should be referred to a (pediatric) gastroenterologist.

As is the case for any AE occurring during the study, for chronic/recurrent GI AEs, the investigator may use discretion anytime to request consultation from an outside physician or additional testing to assist in the diagnosis or management of the AE.

If a subject is seen by a gastroenterologist, the study site will attempt to procure records of the visit as well as any test results including those from endoscopy and endoscopic biopsy, if performed. These results will be retained with the subject's medical notes.

8.1.4.3 Accidental and Nonaccidental Food Allergen Exposures

An accidental food allergen exposure is any known or suspected exposure to a food to which the subject is allergic, including peanut, whether or not it results in an AE. A nonaccidental food allergen exposure is an intentional exposure to a food to which the subject is allergic, including peanut, whether or not it results in an AE.

Subjects will be instructed to contact the site study coordinator or investigator after any known or suspected food allergen exposure, even if it does not cause symptoms. The subject may be asked to return to the site. These events will be reported as follows:

• The nonserious AEI form will be completed for each of these events, in addition to events where consumption of peanut without a reaction occurs, *unless*:

ARC008 Protocol Amend 6.0

• The accidental/nonaccidental food ingestion safety event meets the definition of an SAE as defined in Section 8.1.3, in which case the SAE form will be completed.

If an accidental/nonaccidental food allergen exposure does not result in an AE, no assessment of severity, seriousness, or relatedness is required.

8.1.4.4 Severe Adverse Events

Any AE meeting the criteria for severe as defined in Section 8.2.2.1 will be reported as an AEI.

8.1.4.5 Adverse Events Associated With Use of Epinephrine

Adverse events may result in epinephrine use. Upon awareness of such an event, site staff will report it within 24 hours using the AEI form, independent of severity or relatedness, or whether it was administered at the study site or at home. If the epinephrine was used for an allergic reaction that meets criteria for anaphylaxis, an accidental/nonaccidental food allergen exposure, a severe AE, or an SAE, the use need not be reported separately. The intent of this AEI is to record events that do not fall into one of the other categories.

8.1.5 Unexpected Adverse Event

An AE is unexpected when its nature, severity, or specificity is not consistent with applicable product information such as safety information provided in the package insert, the investigational plan, the investigator brochure, or the protocol. The reference safety information for assessment of expectedness of serious adverse reactions to AR101 for reporting purposes is provided in the AR101 investigator brochure.

8.1.6 Clinically Significant Laboratory Results

An abnormal test result usually warrants reporting as an AE in the following situations:

- The test result is associated with clinical symptoms or signs, and/or
- The test result requires additional diagnostic testing or medical/surgical intervention, and/or
- The test result leads to a change in dosing or discontinuation of study treatment.

8.2 Adverse Event Monitoring and Recording

8.2.1 Monitoring Procedures

All AEs will be recorded from the time of signing of the ICF through at least 14 days after the last AR101 dose, 14 days after the last food challenge, or until resolution or stabilization of all AEs ongoing at the time dosing is stopped, whichever is later. In the event the ICF for

ARC008 is signed before the prior study exit visit, AEs will be recorded from the time of the Screening/Baseline visit.

The investigator will treat subjects experiencing AEs appropriately and observe them at suitable intervals until their symptoms resolve or their status stabilizes.

Any new event or experience that was not present at Screening/Baseline or worsening of an event present at Screening/Baseline will be reported as an AE. Unchanged, chronic conditions are not AEs and should not be recorded on the AE form of the eCRF.

AEs may be discovered through any of the following methods:

- Observing the subject
- Questioning the subject, which should be done in an objective manner
- Receiving an unsolicited complaint from the subject
- Review of medical records/medical notes

8.2.2 Recording Procedures

All AEs will be recorded in the source documents from the time of signing of the ICF through at least 14 days after the last AR101 dose or last food challenge, whichever is last. In the event the ICF for ARC008 is signed before the prior study exit visit, AEs will be recorded from the time of the Screening/Baseline visit. Recording of these AEs into the eCRF is described in the eCRF completion guidelines.

Any event that meets the definition of an SAE (Section 8.1.3) will also be reported to the study Safety Reporting Center using an SAE report form as described in Section 8.3 in addition to completing the AE form. SAE follow-up reports should include, as applicable, hospital admittance notes, hospital discharge summary, clinical notes, resolution date, treatment, and any other pertinent information regarding the event. Reporting should not be delayed in order to provide these documents. In the event of a death, other supporting data (death certificate, medical notes, etc) should be included. Source documents, with subject identifiers redacted, can be scanned and attached to the AE form as well.

AE Type	Form	Reference Section
All AEs	eCRF	8.2.1-8.2.2
SAE	SAE Form	8.1.3
AEI	AEI Form	8.1.4.1-8.1.4.5
Pregnancy	Pregnancy Form	8.1.1

AE = adverse event; AEI = adverse event of interest; eCRF = electronic case report form; SAE = serious adverse event.

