8.3 Serious Adverse Event Reporting Procedures

All SAEs will be reported to the sponsor from the time of signing of the ICF through at least 14 days after the last AR101 dose or last food challenge, whichever is last. SAEs will be recorded in the electronic data capture (EDC) system. The site will also report an SAE to the Safety Reporting Center within 24 hours of the site's knowledge of the event using an SAE report form.

If the ICF for ARC008 is signed before the prior study exit visit, SAEs will be reported in the prior study until the time of the Screening/Baseline visit in ARC008. Thereafter, SAEs will be reported in ARC008.

If the investigator becomes aware of an SAE with a suspected causal relationship to AR101 that occurs within 30 days after the last AR101 dose, the investigator will report it to the sponsor.

The following attributes will be included in an SAE report:

- Description
- Date of onset and resolution (if known when reported)
- Severity
- Assessment of relatedness to test article
- Action taken

The investigator will apply clinical judgment to determine whether an AE is of sufficient severity to require discontinuation of AR101. If necessary, an investigator will suspend any study procedures and institute the necessary medical therapy to protect a subject from any immediate danger.

Subsequent review by regulatory authorities, the sponsor's internal safety risk management team, IRBs/ECs, or the sponsor may suspend further study treatment or procedures at a site. The study sponsor and the regulatory authorities retain the authority to suspend additional enrollment and treatments for the entire study as applicable.

Allergic reactions during food challenges that meet the criteria for serious will be reported as related to the procedure.

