Maintenance	2, 3, and 5	The day following the date of first in- clinic dose of 300 mg during the Up- Dosing period. For subjects who did not enter the Up-Dosing period: the date of first Initial Maintenance Visit.	Date of last dose of study product
Follow-Up Observation	All (1-5)	The day following the date of last dose of study product	Date of Study Exit visit. For subjects without a date of Study Exit visit: the date of study completion.
Overall	All (1-5)	Date and time of first in-clinic or at home dose of treatment in ARC008	Date of Study Exit visit. For subjects without a date of Study Exit visit: the date of study completion.

Table 4Study Period Definitions

- The active treatment period is defined as the time period beginning with the date and time of the first dose of study product and ending with the date and time of the last dose of study product.
- Duration of active treatment period (days) for AR101 is calculated as the date of last dose minus the date of first dose of AR101 plus 1.

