7.5. MISSING DATA

All AEs, unless occurring during an OLFC, real world peanut challenge (RWPC), or DBPCFC, with partial/missing dates and times will be considered TEAEs unless a partial date clearly indicates that it occurred prior to first dose of AR101 in ARC008 or more than 30 days after the last dose of treatment. All therapies with partial or missing dates and times recorded on the Concomitant Medication or Non-Drug Therapy CRF pages will be considered concomitant unless a partial stop date and time clearly indicates it was stopped prior to the first dose of AR101 including parent studies. Start and stop dates will be imputed, to determine TEAEs and concomitant medications, as described below. No imputation will be done for a completely missing stop date or for subjects who did not receive study treatment.

Start dates with a missing day but which have month and year populated will be imputed such that:

- For TEAEs, if the provided month and year match the month and year for that subject's date of first dose of AR101 in ARC008, then the Day 1 date will be used
- For concomitant medications, if the provided month and year match the month and year for that subject's date of first dose of AR101 including parent studies, then the date of first dose of AR101 including parent studies will be used
- In all other cases the 1st of the month will be used with the provided month and year

Start dates with a missing day and month but which have year populated will be imputed such that:

- For TEAEs, if the provided year matches the year for that subject's date of first dose of AR101 in ARC008, then the date of first dose of AR101 in ARC008 will be used
- For concomitant medications, if the provided year matches the year for that subject's date of first dose of AR101 including parent studies, then the date of first dose of AR101 in including parent studies will be used
- In all other cases the 1st of January will be used with the provided year

For TEAEs, start dates that are completely missing will be imputed as the date of first dose of AR101 in ARC008 (Day 1). For concomitant medications, start dates that are completely missing will be imputed as the date of first dose of AR101 including parent studies.

Stop dates will be imputed as follows:

• Missing day with a provided year and month will use the last day of the month

• Missing day and month with provided year will use December 31

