9.1. ADVERSE EVENTS

TEAEs will be summarized excluding symptoms recorded during the food challenges.

AEs will be classified by severity using the Consortium of Food Allergy Research (CoFAR) grading system for allergic reactions, modified European Academy of Allergy and Clinical Immunology (EAACI) guidelines for anaphylactic reactions, and Common Terminology Criteria for Adverse Events (CTCAE) for all other AEs, all as per Section 8.2.2.1 of the protocol.

If symptoms are recorded as part of an anaphylactic reaction, only the single anaphylactic reaction event will be summarized and not the individual symptoms.

All reported AEs will be classified into SOC and PT using MedDRA version 26.0.

TEAEs are defined as those AEs with onset after the first dose of AR101 in ARC008 and no more than 30 days after the last dose of study drug. Non-TEAEs will be listed by treatment pathway and subject ID; these events will not be summarized. TEAEs will be summarized for the Safety Population by study period as follows:

- Initial Escalation
- Up-Dosing
- Initial and Extended Maintenance
- Overall (Initial Escalation, Up-Dosing, and Initial and Extended Maintenance)

Summaries that are displayed by system organ class and preferred terms will be ordered by descending incidence of system organ class and preferred term within each system organ class. Summaries displayed by preferred term only will be ordered by descending incidence of preferred term. Summaries of the following types will be presented:

• Overall summary of the number of unique TEAEs and TESAEs and subject incidence of TEAEs and TESAEs meeting various criteria;

- Overall summary of the number of unique TEAEs and TESAEs and subject incidence of TEAEs and TESAEs meeting various criteria by total exposure including parent studies;
- Subject incidence of TEAEs by MedDRA system organ class and preferred term;
- Subject incidence of TEAEs by severity grade, MedDRA system organ class, and preferred term;
- Subject incidence of grade ≥ 3 severity TEAEs by MedDRA system organ class and preferred term;
- Subject incidence of TESAEs by MedDRA system organ class and preferred term;
- Subject incidence of TEAEs leading to discontinuation of study product by MedDRA system organ class and preferred term;
- Subject incidence of TEAEs leading to discontinuation of study product by total AR101 exposure including parent studies, MedDRA system organ class, and preferred term;

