9.2.1. Anaphylaxis

Anaphylactic AEs will be considered AEIs. Anaphylaxis is defined by a number of signs and symptoms that occur alone or in combination within minutes up to a few hours after exposure to a provoking agent. The severity of the reaction will be assessed according to the EAACI system for grading the severity of anaphylactic reactions (Muraro, 2007).

All reported anaphylactic reaction episodes will be listed by treatment pathway and subject.

Each anaphylactic reaction will be identified by the following triggers:

• Study product/Investigational product (IP)

- Peanut or peanut-containing food
- Other food allergen
- Medication
- Insect sting
- Environmental allergen(s)
- Other
- Unknown

Treatment-emergent anaphylactic reactions include anaphylactic reactions that occur after first dose of AR101 in ARC008 through 30 days after last dose of study product, but excluding anaphylactic reactions that occur during or related to a food challenge. Treatment-emergent anaphylactic reactions will be summarized in the Safety Population separately for the following study periods:

- Initial Escalation
- Up-Dosing
- Initial and Extended Maintenance
- Overall (Initial Escalation, Up-Dosing, and Initial and Extended Maintenance)

Summaries of each study period will include:

- The number of anaphylactic reactions.
- The number of anaphylactic reactions by trigger, study product, peanut or peanutcontaining food, other food allergen, medication, insect sting, environmental allergen, other and unknown.
- Incidence of subjects experiencing an anaphylactic reaction by number of episodes, subjects experiencing an anaphylactic reaction by severity using modified EAACI guidelines, subjects experiencing an anaphylactic reaction that was a SAE, subjects experiencing an anaphylactic reaction that required epinephrine use, the location of epinephrine episodes (home or study site), and the individual symptoms involved.

The above summary will be produced for all treatment-emergent anaphylactic reactions, all treatment-emergent anaphylactic reactions by total AR101 exposure including parent studies, and for treatment-related anaphylactic reactions. Anaphylactic reactions will also be listed by treatment pathway, subject ID, and episode date.

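### TEAEs are counted to 30 days after the last dose, but post-dose events fall in no tabulated treatment period, the SAP defines Overall in two ways, and general AE recording is guaranteed for only 14 days

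*Protocol*

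**What the plan says.** **Analysis window.** SAP 9.1 defines TEAEs as AEs "with onset after the first dose of AR101 in ARC008 and no more than 30 days after the last dose of study drug". The missing-date rule in SAP 7.5 uses the same limit: an AE with a partial date stays treatment-emergent unless the date clearly places it before the first dose or "more than 30 days after the last dose of treatment". SAP 9.2.1 counts anaphylactic reactions "through 30 days after last dose of study product", and SAP 9.2.3 sets the same limit for food allergy episodes.

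**Display.** SAP 9.1, 9.2.1 and 9.2.3 each list four columns: Initial Escalation, Up-Dosing, Initial and Extended Maintenance, and an Overall spelled out as those three. Table 4 ends Initial and Extended Maintenance on the date of the last dose and starts Follow-Up Observation on "The day following the date of last dose of study product". Table 4 also has its own Overall row, which runs to the Study Exit visit or, failing that, to study completion.

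**Collection.** Protocol 8.2.2 requires all AEs to be recorded "through at least 14 days after the last AR101 dose or last food challenge, whichever is last". Protocol 8.2.1 adds an extension, "or until resolution or stabilization of all AEs ongoing at the time dosing is stopped, whichever is later", which concerns AEs already present when dosing stops. The closing telephone contact (Protocol 7.1.3 and its counterparts for the other pathways) has the same 14-day minimum. Protocol 8.3 adds a duty to report any "SAE with a suspected causal relationship to AR101 that occurs within 30 days after the last AR101 dose" of which the investigator becomes aware. Protocol 3.2.7 schedules calls at 3, 6 and 9 months covering a list of key events and SAEs.

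**The concern.** The primary objective expressly includes safety after the last dose (SAP 2.1), and the frequencies of AEs, anaphylaxis and food allergen exposure are primary endpoints (SAP 3.1). A table headed as treatment-emergent to 30 days tells its reader that those 30 days were both observed and counted.

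Two things stand in the way. First, an event can meet the TEAE definition and have no treatment-period column to go into, and whether it reaches Overall depends on which section of the SAP the programmer follows. Second, for ordinary new AEs the protocol guarantees less than half of the post-dose window. Later capture depends on how far past day 14 each site makes its call, so it may be uneven between sites.

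**Working it through.** The study is descriptive and has no sample size, power or alpha to reproduce. The check is a trace through the SAP rules followed by day arithmetic.

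**1. Tracing a post-dose event.** Take a subject in Treatment Pathway 1 whose last dose is on day D and who has a new AE on day D+10.

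- SAP 9.1 definition: 10 is not more than 30, so it is a TEAE.
- Table 4, Initial and Extended Maintenance: ends on D, so the event is outside.
- Table 4, Follow-Up Observation: starts on D+1, so the event is inside, but this period is not a column.
- Overall as worded in SAP 9.1 (the three treatment periods): outside.
- Overall as defined in Table 4 (to Study Exit): inside.

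The same happens to a Pathway 3 subject who stops on Initial Escalation Day 1. That period closes at the end of the day, Up-Dosing never opens, and an event the next day is a TEAE with no treatment column. Two programmers who each follow one section would report different Overall counts.

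**2. Days without guaranteed recording of new general AEs.** Let L be the days from last dose to last food challenge. The documents supplied do not give L, so a range is shown.

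Gap = max(0, 30 − (14 + L))

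| L (days, assumed) | Recording guaranteed to day | Gap (days) |
|---|---|---|
| 0 | 14 | 16 |
| 1 | 15 | 15 |
| 2 | 16 | 14 |
| 7 | 21 | 9 |
| 14 | 28 | 2 |
| 16 | 30 | 0 |

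At L = 0 the share is 16/30 = 53%. Dosing continues up to the last challenge, the DBPCFC takes 2 days, and AR101 is not given on those days (Protocol 6.2.3, 7.1.3). L is therefore probably about 1 or 2 for subjects who have the challenge. Subjects who stop early for safety reasons have no challenge at End of Treatment, so L = 0 and the full 16 days apply to them.

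**3. Size relative to a subject's whole TEAE window.** With T treated days in ARC008, the window is T + 30 days. The share without guaranteed general recording is 16/(T + 30) at L = 0. The share outside the three treatment periods is 30/(T + 30).

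| Treated time | 16/(T + 30) | 30/(T + 30) |
|---|---|---|
| 2 days | 16/32 = 50% | 30/32 = 93.8% |
| 28 days | 16/58 = 28% | 30/58 = 51.7% |
| 1 year (365.25 days) | 4.0% | 7.6% |
| 3 years | 1.4% | 2.7% |
| 5 years | 0.9% | 1.6% |

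These are shares of time, not of events. The documents give no post-dose AE rate from which a number of events could be computed.

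**The case against.** The strongest reply is that the post-dose window is far from empty. Fourteen days is a minimum, and nothing forbids recording later events. AEs ongoing at the last dose are followed to resolution or stabilization, and subjects who stop for chronic or recurrent GI AEs are followed monthly for at least 6 months (Protocol 4.4.2). The call at 3 months reaches back over days 15 to 30. It asks about systemic allergic reactions, EoE, food allergen exposures, epinephrine use, hospitalizations and emergency visits of any cause, and SAEs. All TEAEs also appear in the listings (SAP 9.1), and the study makes no formal comparison.

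All of this stands, and it rules out two readings that a reader might infer. One is that only SAEs thought to be related are captured on days 15 to 30, so that the data lean towards related events. The 30-day rule in Protocol 8.3 is limited in that way, but the follow-up calls are not, and they include non-serious key events. The other is that no non-serious AE is collected after day 14. The unguaranteed part is narrower: new AEs that are neither serious nor on the key-event list.

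A third tempting reading is that post-dose TEAEs are dropped from every table. The Overall row of Table 4 would include them, so the SAP contains an unresolved conflict and not a settled omission. The reply does not remove that conflict, and it does not supply a treatment-period column for these events.

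**Conclusion.** The point holds as a minor one with three parts. Events on all 30 post-dose days lie outside every tabulated treatment period. SAP 9.1 and Table 4 give incompatible definitions of Overall for primary safety endpoints. Recording of new general AEs is guaranteed for 14 of the 30 days when no challenge follows the last dose, and for about 15 or 16 days when the last challenge falls 1 or 2 days after it.

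The effect on a subject treated for 5 years is under 1% of the window for collection and 1.6% for display. It is material only for subjects who stop in Initial Escalation or early Up-Dosing, where the post-dose days make up half or more of the window.

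This rests on the main texts alone. The protocol appendices, the eCRF completion guidelines and the table shells were not available, and any of them might already settle how Overall is built or how late AEs are entered. The values of L are assumptions.

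**What to change.** In SAP 9.1, 9.2.1 and 9.2.3:

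- Assign events on days 1 to 30 after the last dose either to the subject's last treatment period or, more transparently given the primary objective, to a separate post-dose column.
- Use one definition of Overall that includes these events, and align it with Table 4. The 30-day limit in the TEAE definition already prevents later follow-up events from entering.
- State with the tables that general AEs on days 15 to 30 were not systematically collected, while SAEs and key events were asked about in follow-up. A sensitivity count limited to 14 days after the last dose or last challenge could be added.

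Two other remedies are less useful. Moving the closing call to day 30 cannot change the data, because SAP Version 2 was written after database lock (SAP 1.1). Cutting the TEAE window itself to 14 days would discard events that were collected and would break alignment with the 30-day windows for anaphylaxis and food allergy episodes.

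The cost is one column or footnote per table and slightly changed TEAE counts. Because Version 2 confines its updates to Appendix A, the change needs a further SAP version or a description in the clinical study report, identified as made after lock.
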